4.1 Study Duration

Each participant will complete 2 sessions. The first session will take 1-2 hours and the second session will take 0.5-1 hour. We expect the entire study to last 3 years (including data analysis).

4.2 Outcome Variables/Endpoints

Behavioral measures of learning: during the learning task, participants will make responses to the stimuli viewed on the computer screen. Responses will be analyzed to assess learning-related effects (e.g., faster responses for predictable displays).

Behavioral measures of memory: during the memory task, participants will make judgments about whether they remember specific displays or sequences of displays. We will analyze their accuracy on these tasks to create a memory score.

Cortisol response: Saliva samples will be collected at multiple timepoints throughout the experiment. These samples will be assayed to quantify levels of the stress hormone cortisol, which will be used to assess basal levels per participant and determine the efficacy of our stress induction.

Alpha-amylase response: Saliva samples will be collected at multiple timepoints throughout the experiment. These samples will be assayed to quantify levels of salivary alpha-amylase, a proxy for the adrenergic stress response. These will be used to assess basal levels per participant and determine the efficacy of our stress induction.

Subjective measures of stress: Subjective ratings of stress will be collected after the stress manipulation to assess individual differences in subjective stress responses.

fMRI BOLD response: For the fMRI experiment, we will be collecting BOLD data for the entire brain during the learning task. Various analyses will be performed on these data to assess neural correlates related to learning and memory.

Gaze/pupil dilation: For the fMRI experiment, we may also collect eye-tracking data during the learning task. Various analyses will be performed on these data to assess proxies for noradrenergic responses and signals related to learning and memory.

Questionnaire responses: Questionnaires such as the Perceived Stress Scale will be scored to assess participants' individual differences in baseline stress levels and determine whether they influence learning and interact with acute stress.

4.2.1 Primary Outcome Variables/Endpoints

To characterize how acute stress affects the relative expression of different kinds of memory, we will measure statistical learning and episodic memory. Statistical learning will be assessed using responses/response times during the learning task, as well as from memory tests (see above). Episodic memory will be assessed by recognition memory performance. We hypothesize that measures of statistical learning will be enhanced following acute stress (as measured, e.g., by greater response time benefits during learning) and that measures of episodic memory (e.g., later recognition) will be diminished following acute stress.

To identify the neural mechanisms by which stress influences these different kinds of memory, we will focus on hippocampal responses measured during fMRI scanning. We hypothesize that measures of functional connectivity between hippocampal subregions CA1 and CA3 will be lower following acute stress (consistent with poorer episodic memory),

Protocol Number [Protocol Number](#) Version Date and Version #

whereas functional connectivity between subregion CA1 and the entorhinal cortex will be higher following acute stress (consistent with better statistical learning).

4.2.2 Secondary and Exploratory Outcome Variables/Endpoints (if applicable)

To assess whether individual differences in the magnitude of the stress response predict the effect of stress on memory, we will leverage both objective and subjective measures of the stress response. We will test whether the change in cortisol and alpha-amylase from pre- to post-stress induction and subjective measures of stress – in addition to baseline levels of stress as measured through questionnaire data – predict the influence of acute stress on our neural and behavioral measures of learning and memory. We will also assess whether anticipatory noradrenergic responses (via pupil dilation) differ with stress and correspond to facilitated learning.

5 Study Participants

5.1 Study Population

Participants in this study will be healthy individuals aged 18-45. We aim to study this healthy, young cohort in order to understand the baseline relationship between stress and memory in neurotypical individuals.

5.2 Number of Participants

Approximately five-hundred participants will be enrolled in the experiments. We plan to run between two and four behavioral studies ($N = 46-138$ each, depending on the exact parameters of the study) and one fMRI study ($N = 100$). These numbers were determined based on power analyses from past studies of statistical learning and episodic encoding (Sherman & [name] 2020) and acute stress effects on memory ([name] et al 2019).

Participants who do not meet our eligibility criteria as confirmed during recruitment (i.e., self-reporting that they are out of the age range or ineligible for MRI studies) will not be included in the participant count. For each participant who is excluded after their participation (i.e., due to responses on an intake questionnaire), we will recruit an additional participant so that the total number of usable participants matched the above-stated desired N s.

5.3 Eligibility Criteria

In order to be eligible for inclusion in the study, and individual must meet all of the following criteria: (1) 18-45 years old, (2) fluent in English, (3) BMI between 18-35.

Any individual who meets any of the following criteria will be excluded from participation in this study: (1) meeting current DSM-V criteria for any substance use disorder (except caffeine), (2) having current significant medical conditions or psychiatric symptoms requiring medication, (3) current use of medications/drugs that interfere with physiological stress responses, (4) peri and post-menopausal women, pregnant or lactating women, and those with hysterectomies, (5) metal in body (for MRI safety). Menstrual cycle status and detailed history will be assessed for female participants.

5.4 Recruitment Procedures

Participants will be identified by responding to flyers (see Appendix 1 & Appendix 2), to a web or social media posting, or by filling out a form on our lab website. Prospective participants will be contacted via e-mail and/or a phone call to confirm their interest and eligibility and schedule a session. Only study personnel listed in this protocol will recruit participants.

We will send prospective MRI participants the MRI safety screening and consent forms via Yale's HIPAA-aligned instantiation of Qualtrics. Prior to scheduling an fMRI session, we will ask the participant if they would have to indicate "yes" to any of the exclusions on the screening form. If so, we will ask follow-up questions about this item to determine whether they are eligible to participate. This advance screening is intended to avoid scheduling fMRI sessions for participants who will be ineligible. Participants will be told that it is optional for them to respond to these questions over email or phone, and that we can schedule an in-person (non-fMRI) session to review the forms instead. All participants will fill out and sign the forms via Qualtrics when they come in for a session. For individuals who are deemed ineligible, all information will be destroyed immediately.

Eligible participants will be offered the option of being a "back-up" participant, in which case they would arrive at the same time as an already-scheduled participant, in addition to directly

Protocol Number [Protocol Number](#) Version Date and Version #

booking their appointments. All participants will provide consent upon arrival at their first scheduled study visit.

5.5 Consent/Accent Procedures/HIPAA Authorization

Only study personnel listed in this protocol will obtain consent. During the session (upon arrival to the study site), participants will receive and sign the consent form via Yale's HIPAA-aligned instantiation of Qualtrics.

Consent forms will describe in detail the study intervention, study procedures, and risks. Written documentation of informed consent is required prior to starting any study procedures. Consent forms will be IRB-approved and the participant will be asked to read and review the document. Back-up participants will be given a separate consent form explaining the procedures and compensation.

The person obtaining consent will ensure that the potential subject is able to read and comprehend the consent. Comprehension will be assessed throughout the consent process and the participant will be given multiple opportunities to ask questions. The investigator will not enroll any participants who are determined to have limited decision-making capacity. They will have the opportunity to ask questions before and during the session. It will be stressed that any participation is voluntary and that consent can be withdrawn at any time. The conversation will take place in a private room to assure the participant's privacy. To avoid coercion, financial incentives for participation will be in line with standard subject payments. A copy of the informed consent document will be given to the participants for their records.

For online studies, participants will be presented with an online version of the consent form. They will be given as much time as they need to read the procedures, and they will indicate their consent by clicking an "I consent" button.

6 Study Methods/Procedures

6.1 Study Procedures

Each experiment will take place across two sessions on two consecutive days. The two sessions will occur 24h apart and will each be conducted between 12-6pm to control for circadian fluctuations in cortisol levels (Lupien et al 2007). Participants will be recruited via the procedures described in 5.4.

On Day 1, participants will be greeted by a member of the study personnel and consent will be obtained. Participants will be randomly assigned to either the Stress group or the Control group. Participants will become acclimated to the study environment and complete intake questionnaires. Participants will then provide a saliva sample (#1) to determine basal levels of cortisol and alpha-amylase. Participants randomly assigned to the Stress group will then undergo the cold pressor test (arm submerged in 0-2C cold water for 3 minutes), while participants in the Control group will have their arm submerged in warm water (37-40 C) for 3 minutes. Participants in the Stress group may be informed that they will be video recorded during the task. Then, a second saliva sample (#2) will be acquired.

Participants will then undergo a brief rest period to allow for the cortisol stress response to emerge (Shields et al., 2017). The duration of this rest period may differ across experiments so that we can assess the influence on the delay between stress and learning on subsequent outcomes. Participants will sit silently or watch a neutral video during this period. If participants are enrolled in the MRI study, we may collect anatomical and resting state fMRI scans during this time.

Following this rest period, an additional saliva sample will be taken (#3), and participants will complete the behavioral learning task. Participants will be exposed to a series of displays on the computer screen (see section 4) and be asked to make responses on a computer interface. After they complete the behavioral task, they will give one more saliva sample (#4), and then be dismissed for Day 1.

Day 2 will take place 24 hours later. Participants will again be greeted by a member of the study personnel. After giving another saliva sample (#5), they will then complete a series of memory tests. Following the test, they will give a final saliva sample (#6). The procedures of the study will then be explained to the participant, and the participant will be given the opportunity to ask questions about the study design. The participant will then be compensated for their participation.

Research staff will be responsible for implementing the interventions and collecting participant data. All study personnel will complete required human research protections training prior to the initiation of participant recruitment, and be trained on study protocols, recruitment and consenting, intervention and/or data collection procedures, and data handling and confidentiality. A Standard Operating Procedures manual will be developed to guide the conduct of the study and used in training. The PIs will supervise junior staff and provide re-training in the study protocol as needed.

Online studies will follow a similar procedure, excluding the Cold Pressor Test and saliva samples (i.e., they will answer intake questionnaires and perform the learning and memory tests). Online studies may follow the two day procedure as described above, or all procedures may be done in a single session. Additionally, online participants will not be assigned to stress or control groups; we will examine how individual differences in stress (as measured via questionnaire data) influence learning and memory.

Protocol Number [Protocol Number](#) Version Date and Version #**Visit Schedule Table**

	Recruitment (Pre-consent)	Visit 1 Day 1	Visit 2 Day 2
Review Eligibility	X		
Informed Consent		X	
Demographics		X	
Questionnaires		X	X
Saliva Samples		X	X
Behavioral Tasks		X	X
fMRI Scanning and eyetracking (if applicable)		X	
Randomization		X	
Adverse Events Reporting (if applicable)		X	X

Protocol Number [Protocol Number](#) Version Date and Version #

6.1.1 Data Collection

Questionnaire and demographic data will be collected using Yale's HIPAA-aligned instantiation of Qualtrics. Please see section 4 (*Intake Procedures*) for a list of the validated questionnaires that will be used. Licensure/training is not required for the administration of these questionnaires.

Behavioral responses will be made on a computer and responses will be recorded with custom experiment programming software designed through Matlab's Psychtoolbox (Brainard, 1997) or Python's Psychopy (Peirce, 2007), programs widely used in psychological research. MRI data will be acquired on the Siemens's 3T Prisma Scanner at the BIC or BrainWorks. Data for online studies will be completed on participants' personal computers, and will be accessed through the Prolific or mTurk interface. Responses will be recorded with custom experiment programming software designed through Javascript.

All data will be coded in a de-identified manner and stored in password-protected computer files accessible only to the research team. fMRI data will be stored on the secured and HIPAA-aligned Milgram computer cluster managed and certified for compliance by the Yale Center for Research Computing. Backups of the fMRI data may be burned to DVDs at the scanner and locked in a cabinet in the [name] lab space. Behavioral data (e.g., button presses, verbal reports, eye-tracking images) will either be recorded on computers secured in the control room and transferred on an encrypted and passcode-protected flash drive to computers in the [name] lab or on a password-protected laptop computer with full disk encryption, which will otherwise be kept locked in the [name] lab space. All video data collected during the behavioral task will be discarded without being looked at within seven days of a participant's participation.

Correspondence with study participants and a spreadsheet linking participant ID codes with identifiable information will be kept on a password-protected desktop computer with full disk encryption in the locked research coordinator office in the [name] lab space. Paper consent forms will be stored separately from any data and in a locked cabinet in the [name] lab space. Electronic consent forms and demographic forms will be stored on the secure Yale Qualtrics server, a HIPAA-aligned tool for survey data collection.

6.2 Method of Assignment/Randomization (if applicable)

Participants will be pseudo-randomly assigned to the experimental groups such that the groups do not differ in age and sex. There will be no blinding procedures, as both the experimenter and participant will be aware of whether they are receiving the cold or warm water treatment.

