6.6 Locations/Facilities

Some behavioral studies will take place in Sheffield-Sterling-Strathcona (SSS) Hall ([name]) or [name] and some will be conducted online, on mTurk or Prolific.

The fMRI studies will take place in the FAS Brain Imaging Center in Dunham Lab ([name]) or BrainWorks ([name]).

7 Statistical Design

The general statistical approach involves examining differences in our outcome measures as a function of stress condition (i.e., whether participants experience acute stress prior to the learning task or not). Analyses will primarily be conducted with repeated-measures ANOVAs (rmANOVA) and t-tests where appropriate.

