7.2 Planned Analyses

We will test the hypotheses that: (1) stress enhances statistical learning (rmANOVA; facilitated reaction time for predictable items during learning in the Stress vs No Stress group); (2) stress enhances retention of statistical learning (*t*-test; better discrimination of *AB* category pairs in the Stress vs No Stress group); and (3) stress impairs episodic memory (*t*-test; overall lower exemplar recognition memory in the Stress vs No Stress group). Although there may be a global effect of worse episodic memory in the Stress group, we expect such deficits to be driven in part by an interaction with category type (*A*, *B*, or *X*). That is, if Stress potentiates statistical learning, these participants would quickly learn to anticipate the *B* category while viewing the preceding *A* category item. Thus, rather than focusing on encoding the *A* category item, they would be predicting the *B* category, leading to greater competition between encoding and statistical learning (rmANOVA; greater deficits in memory for *A* relative to *X* items in the Stress group).

For the fMRI experiment, we will investigate the neural mechanisms underlying stress effects on different forms of learning using a combination of *connectivity*, *multivariate*, and *univariate* approaches. Specifically, we will test the working hypothesis that stress will have opposite effects on neural processes supporting episodic encoding and statistical learning. Based on rodent models, we hypothesize that stress will facilitate the function of subregions and connections associated with the monosynaptic pathway (MSP) while impairing or sparing the function of the trisynaptic pathway (TSP).

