We will test whether *stress induces state-level changes in TSP and MSP connectivity* by comparing background connectivity (Al-Aidroos et al., 2012) from CA1-entorhinal cortex (MSP) and CA1-CA2/3/DG (TSP) in Stress vs. No Stress participants. If state-level changes are not detected, we will use a different connectivity approach to separate connectivity patterns during different trial types. To probe the functional significance of connectivity changes, we will perform our recently developed seed connectome-based predictive modeling analysis ([name] et al., 2020), using whole-brain CA1 connectivity during encoding to predict subsequent memory performance in Stress and No Stress participants. To test whether *stress amplifies neural signatures of statistical learning*, we will use multivariate approaches to characterize neural evidence of prediction. Following prior work (Sherman & [name], 2020), we will train a classifier in the hippocampus (using a linear support vector machine implemented in Python's scikit-learn module) to distinguish between

Protocol Number [Protocol Number](#) Version Date and Version #

different scene categories. By training the classifier on voxel patterns in the hippocampus from the localizer run (in which no statistical regularities are present) to distinguish amongst B categories, we can derive a signature of B category to apply to learning runs. The extent to which B can correctly be classified during the preceding A item (when B has not yet been presented) serves as a neural measure of prediction. If stress amplifies neural signatures of statistical learning, we expect to see greater evidence for the predicted category in the Stress, relative to No Stress, group. Finally, univariate whole-brain analyses will include subsequent memory analyses (Wagner et al., 1998) (contrasting Remembered with Forgotten trials from conditions A/B/X) to *test how whole brain processes supporting memory differ* in Stress vs No Stress participants.

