7.2.1 Secondary Objective Analyses (if applicable)

Further exploratory analyses will investigate whether stress-induced changes in learning and memory are associated with the magnitude of the stress-induced cortisol and adrenergic response by using these measures as covariates in the above analyses. We hypothesize that larger stress-induced increases in cortisol are associated with stronger benefits for statistical learning and impairments for episodic encoding. In the fMRI study, we will test whether stress exposure modulates stimulus-evoked and ITI-evoked pupil dilation, processes previously been shown to be modulated by stress exposure and associated with subsequent episodic memory (Henckens et al 2009; Qin et al 2012), although the role of pupil reactivity in statistical learning is unclear.

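### Age and sex are balanced at assignment but left out of the between-person Stress vs No Stress tests; adding them is an optional, cheap gain in power if they predict the outcome.

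*Combined protocol and SAP*

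**What the plan says.** Section 6.2 describes constrained assignment: "Participants will be pseudo-randomly assigned to the experimental groups such that the groups do not differ in age and sex". It names no algorithm and does not say how close the balance must be.

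The opening of section 7 sets the general method: "Analyses will primarily be conducted with repeated-measures ANOVAs (rmANOVA) and t-tests where appropriate". Section 7.2 then plans these group comparisons of one value per person:

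- retention of statistical learning, by t-test on discrimination of AB "category pairs in the Stress vs No Stress group";
- episodic memory, by t-test: "overall lower exemplar recognition memory in the Stress vs No Stress group";
- background connectivity "from CA1-entorhinal cortex (MSP) and CA1-CA2/3/DG (TSP) in Stress vs. No Stress participants", which is two pathway measures;
- classifier evidence for the upcoming category: "we expect to see greater evidence for the predicted category in the Stress, relative to No Stress, group".

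No age or sex term is attached to any of them. The only covariates named in the plan are the hormone responses in section 7.2.1, where exploratory analyses ask whether learning effects are "associated with the magnitude of the stress-induced cortisol and adrenergic response by using these measures as covariates in the above analyses". Age is recorded at intake (section 4, Intake Procedures), and the assignment rule needs both age and sex.

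**The concern.** When groups are balanced on a factor that predicts the outcome, the true sampling variance of the group difference falls. A pooled t-test leaves that factor's variance in its error term, so its standard error is too large. Intervals are then too wide, p-values too big, and power is lost. Putting the balancing factors in the model removes this mismatch. If the factors do not predict the outcome, there is nothing to recover.

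The stake is efficiency only. The error is in the conservative direction, so a positive finding from the planned tests is not put in doubt.

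**Working it through.** **Inputs from the plan (section 7.1).** 46 per condition for the behavioural studies; 40 per group for fMRI, justified by d = .45 and 80% power.

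**Assumptions.** Two-sided 5% (the plan states no alpha). R² of age plus sex from 0 to .20. d = .45 is used for illustration: section 7.1 gives it for neural effects, not for the behavioural tests.

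**The plan's own figure.** For a one-sample or paired test, (1.96 + 0.842)² / 0.45² = 38.8; the t-based answer is 40.7, close to the stated 40. For a two-group comparison, 2 × 38.8 = 77.5, so 78 per group (79 on the t distribution). The stated 40 therefore fits a within-group test. Between groups, power at d = .45 is about 51% with 40 per group and 57% with 46. That shortfall is a separate matter, but it sets the base for the gains below.

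**Closed form, exact balance, 46 per group.** Let s = √(1 − R²).

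- Adjusted power: noncentral t, 2n − 4 = 88 df, noncentrality (0.45/s)√(n/2). At R² = .10: s = 0.949, noncentrality 2.275, power 61.4%.
- Unadjusted power, approximately: 1 − Φ((1.987 − 0.45√23)/s). At R² = .10: 1 − Φ((1.987 − 2.158)/0.949) = 57.2%.
- Unadjusted type I error, approximately: 2(1 − Φ(1.96/s)). At R² = .10: 3.9%.

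| R² | Adjusted power | Unadjusted power | Unadjusted type I error | SE ratio, 1/s |
|---|---|---|---|---|
| 0 | 56.9% | 57.0% (exact) | 5.0% | 1.00 |
| .05 | 59.1% | 57.0% | 4.4% | 1.03 |
| .10 | 61.4% | 57.2% | 3.9% | 1.05 |
| .20 | 66.5% | 57.6% | 2.8% | 1.12 |

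**Simulation.** 60,000 trials per cell; age uniform on 18 to 45, sex 50:50, R² split equally between them. Tight balance means pairs matched on sex and sorted age. Loose balance means an assignment is accepted if age and sex each differ at p > .05. Change in power from adjusting, in points, at d = .45:

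| R² | 46/group, tight | 46/group, loose | 46/group, simple randomisation | 40/group, tight | 40/group, loose |
|---|---|---|---|---|---|
| 0 | -0.05 | -0.59 | -0.94 | -0.14 | -0.79 |
| .02 | 0.71 | -0.01 | 0.03 | 0.71 | 0.11 |
| .05 | 1.95 | 1.55 | 1.02 | 1.99 | 1.26 |
| .10 | 4.24 | 3.63 | 3.34 | 4.11 | 3.70 |
| .20 | 8.77 | 8.52 | 8.77 | 9.05 | 8.38 |

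Simulated unadjusted type I error at 46 per group and R² = .05, .10 and .20 is 4.5%, 3.8% and 2.9% under tight balance. Under loose balance it lies between 4.4% and 5.0% over the whole range. The adjusted test stays at 4.8 to 5.1% in every cell.

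**Sensitivity, 46 per group.** At R² = .05, .10 and .20, d = .30 gains 1.1–1.9, 2.4–3.8 and 6.2–8.2 points; d = .60 gains 1.2–1.3, 2.7–2.9 and 5.0–6.7. Putting all of R² = .10 on age or all on sex leaves the gain at 3.6 to 4.1 points. Break-even is near R² = .02 under loose balance and near 0 under tight balance.

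**As sample size.** Ignoring the lost degrees of freedom, 46/(1 − R²) gives 48.4, 51.1 and 57.5 per group unadjusted at R² = .05, .10 and .20.

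**The case against.** The strongest reply is that no defect is alleged. A t-test after balanced assignment is valid and at worst conservative, and the whole benefit depends on an R² that the documents do not supply. Section 5.1 describes a healthy, young cohort, in which age and sex may explain little. This stands: nothing in the plan shows that either factor is prognostic, and it is why the point is optional.

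Second, AB-pair discrimination and classifier evidence might be scored within person, against foils or other categories. General age and sex differences would then largely cancel, as they do in the rmANOVA contrasts. The scoring is not specified, so the higher R² rows are the least secure for those two measures.

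Third, the fMRI sample size is not settled: the Synopsis and section 5.2 give 100, section 7.1 gives 80. At 50 per group the unadjusted base is 60.6%, and adjusted power at R² = .05, .10 and .20 is 62.8%, 65.1% and 70.2%. The base moves, but the gain (2.2, 4.5 and 9.6 points) is much the same.

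Fourth, most of the gain would arise under simple randomisation too, as the table shows. That is true, and it does not weaken the case for adjusting.

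Finally, adjustment does not repair the low between-group power. For 80% power at d = .45, adjusted tests would still need 74, 70 or 63 per group at R² = .05, .10 or .20. This also stands.

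**Conclusion.** The point holds as an optional improvement. Age and sex enter the design and not the analysis. Adjusting keeps the test at its nominal 5% whether the balance turns out tight or loose, and it recovers power if the factors are prognostic: about 4 points at R² = .10 and 8 to 9 at .20, but 2 points or less at .05 and below. If they are not prognostic, the loss under balanced assignment is 0.0 to 0.6 point at 46 per group and 0.1 to 0.8 at 40 per group. Under simple randomisation it is about 1 point.

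These sizes rest on the assumed R², the illustrative d, two-sided 5%, and an even spread of age and sex. Replacing excluded or incomplete participants (sections 5.2 and 7.7) may loosen the planned balance, which is a mild further reason to fix the covariates in advance.

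The point does not reach the rmANOVA within-person contrasts, the whole-brain analysis "contrasting Remembered with Forgotten trials from conditions A/B/X", the connectome-based prediction, or the online studies, which have no stress assignment.

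**What to change.** In section 7.2, replace the two behavioural t-tests (AB-pair discrimination and overall exemplar recognition) with a linear model containing group, sex and continuous age. Use the same covariates for the group comparisons of the two background-connectivity measures and of classifier evidence for the predicted category. Name the adjusted result as the main one in advance and report the unadjusted result as a sensitivity analysis, so that the choice cannot follow the data.

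The cost is two degrees of freedom per model, a few lines of text and one extra reported estimate per comparison. No new data or staff are needed.
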